19	BMI	Body Mass Index
20	LAAO	Left Atrial Appendage Occlusion

Summary of the Trial Protocol

Test Name	Evaluation of the Safety and Efficacy of Catheter Ablation After Left Atrial Appendage Occlusion with the WATCHMAN FLX Device
Sponsor	Department of Cardiology, Affiliated Hospital of Nantong University
Principal Investigator	[name]
Purpose of the test	
1. Main Purpose: To evaluate the safety and efficacy of catheter ablation performed one month after WATCHMAN FLX left atrial appendage occlusion (LAAO) in patients with non-valvular atrial fibrillation(AF).
 
2. Secondary Purpose: To investigate the impact of a two-surgery sequential treatment regimen on the recurrence rate of atrial fibrillation, the incidence of stroke, and the quality of life of patients, and to provide evidence-based support for decision-making in the clinical application of combined therapy.

Trial Population	Patients diagnosed with non-valvular AF who are scheduled to undergo sequential LAAO using the WATCHMAN FLX device and catheter-based ablation.
Trial Design	
This study is a prospective, single-arm, multicenter clinical trial designed to evaluate the safety and efficacy of catheter ablation performed one month after LAAO with the WATCHMAN FLX device. Approximately 210 patients with non-valvular AF who meet the indications for both transcatheter LAAO and catheter ablation will be enrolled across 10 research centers in China. The study procedures are outlined as follows: :
 
 Patient Screening and Enrollment: Eligible patients will undergo elective LAAO with the WATCHMAN FLX device (first procedure) after signing the informed consent form (ICF). Postoperative Management: Following the LAAO with the WATCHMAN FLX device, patients will undergo standard anticoagulation therapy for one month. If transesophageal echocardiography (TEE) reveals no device-related thrombosis (DRT) or residual flow >5 mm, the patient will undergo catheter ablation for atrial fibrillation (second procedure) one month after the initial LAAO.

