	
4. Quality of life improvement at 12 months measured by the Atrial Fibrillation Effect on Quality-of-Life (AFEQT) questionnaire: Improvement in quality-of-life score from baseline to 12 months following index ablation or AAD treatment, with a possible score range of 20 to 140 (higher scores indicate worse outcomes).

Entry Criteria	
 1) Age ≥ 18 years with a diagnosis of nonvalvular AF; 2) Eligible for indications for treatment with WATCHMAN FLX LAAO and transcatheter atrial fibrillation ablation; 3) Preoperative imaging evaluation showed that the LAA anatomy was suitable for WATCHMAN FLX device implantation; 4) Patients agreed to participate in the study and signed an ICF.
Exclusion criteria	
Patients meeting any of the following criteria were not eligible for this study:
 
 1) Presence of valvular heart disease or other structural heart disease that causes atrial fibrillation; 2) Preoperative detection of LAA thrombus or acute thrombotic event; 3) The patient has a severe bleeding tendency or a recent major bleeding event (e.g. gastrointestinal hemorrhage, cerebral hemorrhage, etc.); 4) Patients who are unable to complete postoperative follow-up (e.g. life expectancy less than 1 year or poor compliance); 5) Other serious diseases (e.g. liver and kidney failure, active infections, etc.) detected on preoperative examination; 6) Women who are pregnant or breastfeeding.
statistical analysis	
1. Sample size calculation:
 
The sample size was calculated based on the primary endpoint. The primary endpoint of this study was “12-month rate of complete closure of the block after WATCHMAN FLX LAAO (CT assessment).” Hypothesized target incidence $P_0 = 74.3\%$ and test incidence $P_1 = 84.3\%$. The significance level $\alpha = 0.05$ (one-sided) and test efficacy $1 - \beta = 80\%$ were calculated to be 200 cases able to fulfill the hypothesis test. Considering the 5% shedding rate, the total sample size was 210 cases.
 
2. Descriptive Statistics:
 
Patient baseline characteristics (e.g. age, sex, history of AF) were expressed as mean \pm standard deviation or median (quartiles) for continuous variables,

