Annex IV: Atrial Fibrillation Effect on Quality-of-Life

questionnaire (AFEQT)

Atrial Fibrillation Effect on Quality-of-Life questionnaire (AFEQT)	 No  Yes IF yes, please complete the AFEQT

In order to better understand the impact of AF on your health-related quality of life, we would like to ask you to answer the following questions and tick the appropriate box!
 
(1) Palpitations: Panic, rapid heartbeat  Not at all  1  2  3  4  5  6  Extremely
 
(2) Irregular heartbeat  Not at all  1  2  3  4  5  6  Extremely
 
(3) Dizziness and blurred vision  Not at all  1  2  3  4  5  6  Extremely
 
(4) Chest tightness, chest pain  Not at all  1  2  3  4  5  6  Extremely
 
(5) Worried that atrial fibrillation may strike at any time  Not at all  1  2  3  4  5  6  Extremely
 
(6) Worry that atrial fibrillation will worsen the disease in the long run.  Not at all  1  2  3  4  5  6  Extremely
 
(7) Concerns about side effects of drugs  Not at all  1  2  3  4  5  6  Extremely
 
(8) Concerns about interventional procedures such as radiofrequency ablation, surgery, implantation of pacemaker  Not at all  1  2  3  4  5  6  Extremely
 
(9) Worried about the side effects of anticoagulant drugs, such as nosebleeds, bleeding gums when brushing teeth, heavy bleeding or bruising from wounds  Not at all  1  2  3  4  5  6  Extremely
 
(10) Fear that treatment will affect daily life  Not at all  1  2  3  4  5  6  Extremely
 
(11) Recreation, leisure, sports, ability to engage in hobbies and interests  Not at all  1  2  3  4  5  6  Extremely
 
(12) Ability to get along with family members and do things together  Not at all  1  2  3  4  5  6  Extremely
 
(13) Limitations on mobility due to perceived fatigue  Not at all  1  2  3  4  5  6  Extremely
 
(14) Limitations on mobility due to shortness of breath  Not at all  1  2  3  4  5  6  Extremely
 
(15) Sports Exercise  Not at all  1  2  3  4  5  6  Extremely
 
(16) Go fast  Not at all  1  2  3  4  5  6  Extremely
 
(17) Climbing hills/carrying things/climbing stairs at a brisk pace without stopping for a break  Not at all  1  2  3  4  5  6  Extremely
 
(18) Strenuous activities such as lifting heavy furniture, running, and strenuous sports such as squash/tennis/swimming/basketball.  Not at all  1  2  3  4  5  6  Extremely
 
(19) Effectiveness of current therapeutic measures to control housing fibrillation  Not at all  1  2  3  4  5  6  Extremely
 
(20) Effectiveness of therapeutic measures in relieving symptoms associated with atrial fibrillation  Not at all  1  2  3  4  5  6  Extremely

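### The AFEQT endpoint's stated 20–140 range, direction and time origin do not agree with the Annex IV form or the single-arm design (minor)

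*Protocol*

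**What the plan says.** Efficacy endpoint 4 in the Protocol Summary (Secondary endpoint) is "Improvement in quality-of-life score from baseline to 12 months following index ablation or AAD treatment". The same entry then fixes the scale and its direction: "possible score range of 20 to 140 (higher scores indicate worse outcomes").

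Annex IV reproduces the questionnaire. Each of its 20 items carries the same response row: a box for Not at all, boxes 1 to 6, and a box for Extremely. No numerical codes are given for the two end boxes. The last two items are "19) Effectiveness of current therapeutic measures to control housing fibrillation" and "20) Effectiveness of therapeutic measures in relieving symptoms associated with atrial fibrillation".

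On design, the Summary states: "This study is a prospective, single-arm, multicenter clinical trial". Ablation is planned one month after LAAO. AADs appear only as permitted treatment in the 90 days after ablation. The Summary's follow-up list treats the 1-month visit as the time of the second procedure and then lists 3 and 12 months. Section 4.1 labels the last visit as one year after surgery without naming the procedure.

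Section 6.2.2 offers either a chi-square test or a paired t-test for change in quality of life. Section 3.1.2 names quality of life among the secondary purposes.

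**The concern.** The endpoint text fixes a range, a direction and a time origin, and the protocol's own form and design disagree with each. If the score were built as written, a plain sum of the printed boxes would not lie on the stated scale. Two items would also count a good answer as a worse score. A reader of the results would then be told a range and a direction that do not describe the number reported.

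The reference to AAD treatment as an index event suits a trial with a drug comparator, which this trial does not have. The chi-square option does not suit the endpoint either: it is a numeric change in the same patients, and the protocol defines no responder category.

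**Working it through.** **Inputs.** Number of items: 20 (Annex IV). Response boxes per item: 8 as read (Annex IV). Stated range: 20 to 140, higher is worse (Summary, efficacy endpoint 4). Ablation: 1 month after LAAO (Summary, Trial Design).

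**1. Reproduce the stated range.** Sum range = items × lowest code to items × highest code.
- Seven levels coded 1–7: 20 × 1 = 20 to 20 × 7 = 140. This is the stated range.

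**2. Apply the form as printed.**
- Eight boxes coded 0–7: 20 × 0 = 0 to 20 × 7 = 140.
- Eight boxes coded 1–8: 20 × 1 = 20 to 20 × 8 = 160.

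Each coding matches one end of the stated range and neither matches both. With eight boxes, 20–140 results only if two boxes share a code or one box is unused.

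**3. Direction of items 19 and 20.** The 20–140 range requires all 20 items: 18 items coded 1–7 would give 18 × 1 = 18 to 18 × 7 = 126. Assume 1–7 coding, the top box as the bad answer on items 1–18 and the good answer on items 19–20, and no reversal.
- Best possible patient: 18 × 1 + 2 × 7 = 32.
- Worst possible patient: 18 × 7 + 2 × 1 = 128.
- Span from best to worst: 128 − 32 = 96 points, against 140 − 20 = 120 as stated, or 80%.

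Totals of 20 and 140 can still occur, but they no longer mark the best and worst states. A patient whose ratings on both items rise from lowest to highest gains 2 × 6 = 12 points, which the stated direction would read as worsening. With reversal the same answers lower the score by 12.

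The pattern does not depend on the coding. Best and worst are 14 and 126 at 0–7 (full range 0–140), and 34 and 146 at 1–8 (full range 20–160).

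**4. Time origin.** If the visit list counts from LAAO, as its 1-month label suggests, the 12-month visit falls 12 − 1 = 11 months after ablation. The endpoint's time point, 12 months after ablation, falls 1 + 12 = 13 months after LAAO. The two differ by about one month. No AAD group exists to supply the alternative index date.

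**5. Test.** The endpoint is a within-patient difference in a numeric score. The paired t-test fits that. An ordinary chi-square test compares categories between independent groups, and the protocol defines neither categories nor groups for this score.

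**The case against.** **The box count may come from how the form was read.** If either end label is only an anchor without its own box, seven levels remain and 20–140 is correct. That all 20 items show the same pattern does not settle this, because one template would be misread the same way each time. This stands as a caution: the mismatch holds for the form as read and needs a check of the original.

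**Reverse-scoring may be in an SAP or scoring guide.** Such a document may exist and is not available here, so the lack of a reversal rule is not itself an error. What stands is narrower: the protocol states a range and a direction that its own form meets, from best to worst, only if items 19–20 are reversed.

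**Coding offsets largely cancel.** Totals under 0–7 and 1–8 differ by 20 × 1 = 20 points, which drops out of a paired change if one coding is used at both visits. Nothing in the protocol says that centres assign codes separately. This is correct, and it limits the first point mainly to the stated scale. It does not help with items 19–20, whose direction enters the change itself.

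**The time origin is an inference.** Neither the Summary's 12-month visit nor Visit 7 names the procedure it counts from, and efficacy endpoints 1 and 2 also count from ablation. This stands: the one-month gap is a likely reading, not a stated rule.

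**Two stronger readings are tempting.**
- *Items 11–18.* A reader might infer that these also run the wrong way, since "11) Recreation, leisure, sports, ability to engage in hobbies and interests" and "12) Ability to get along with family members and do things together" name an ability and "15) Sports Exercise" names only an activity. The documents do not support that. The English annex looks like a rough translation (see the wording of item 19), and section stems may have been lost, so the text patients actually answer may state a direction.
- *Visit schedule.* A reader might infer that AFEQT was left out of section 4.1. No such row is visible in the text available, but the note markers there skip 7, so a row may have been lost in reading.

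**Conclusion.** The point holds as a minor inconsistency in one secondary endpoint. Three parts stand:
- **Scale.** The eight boxes as read do not produce the stated scale under consecutive coding. This is subject to a check of the original form.
- **Direction.** The stated direction and end points fail for items 19–20 unless they are reversed. The best-to-worst span is then 96 points instead of 120, assuming 1–7 coding and that the other 18 items run as the endpoint says.
- **Time origin and test.** The AAD alternative has no counterpart in the design, and ordinary chi-square does not suit a paired numeric change. The difference between an LAAO and an ablation origin is about one month and should matter little for a mean score.

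Confidence is high on items 19–20 and the AAD wording, and moderate on the box count. No error is asserted in items 11–18 or in the visit table. The primary analysis and sample size are unaffected.

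**What to change.** 1. Check the number of response boxes on the original form, then make the response options, their codes and the stated range agree.
2. State that items 19–20 are reverse-scored. Alternatively, report them separately and restate the range as 18–126 (18 items at 1–7).
3. Delete the AAD alternative from the endpoint, name one time origin, and match the 12-month visit to it.
4. Report the paired mean change with a 95% confidence interval, using the paired t-test already named in section 6.2.2, and drop the chi-square option for this score.
5. Check the original-language form for the direction of items 11–18, and the original section 4.1 table for an AFEQT row. Amend only if either check shows a gap.

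The cost is wording in the endpoint definition, section 6.2.2 with its counterpart in the Summary, and the annex form, plus the checks against originals. If the boxes or stems have to change, the form should be corrected before further use. Nothing changes in the sample size or the primary analysis.

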3.1 Purpose

3.1.1 Main Purpose

To evaluate the safety and efficacy of catheter ablation performed one month after WATCHMAN FLX left atrial appendage occlusion (LAAO) in patients with non-valvular atrial fibrillation (AF).

3.1.2 Secondary Purpose

To investigate the impact of a two-surgery sequential treatment regimen on the recurrence rate of atrial fibrillation, the incidence of stroke, and the quality of life of patients, and to provide evidence-based support for decision-making in the clinical application of combined therapy.

3.2 Selection of subjects

3.2.1 Entry Criteria

- 1) Age ≥ 18 years with a diagnosis of nonvalvular AF;
- 2) Eligible for indications for treatment with WATCHMAN FLX LAAO and transcatheter atrial fibrillation ablation;
- 3) Preoperative imaging evaluation showed that the LAA anatomy was suitable for WATCHMAN FLX device implantation;
- 4) Patients agreed to participate in the study and signed an ICF.

3.2.2 Exclusion criteria

Patients meeting any of the following criteria were not eligible for this study:

- 1) Presence of valvular heart disease or other structural heart disease that causes atrial fibrillation;
- 2) Preoperative detection of LAA thrombus or acute thrombotic event;
- 3) The patient has a severe bleeding tendency or a recent major bleeding event (e.g. gastrointestinal hemorrhage, cerebral hemorrhage, etc.);
- 4) Patients who are unable to complete postoperative follow-up (e.g. life expectancy less than 1 year or poor compliance);
- 5) Other serious diseases (e.g. liver and kidney failure, active infections, etc.) detected on preoperative examination;
- 6) Women who are pregnant or breastfeeding.

4. Study process

4.1 Test flow

Visiting time \ Visiting Program	Visit 1	Visit 2	Visit 3	Visit 4	Visit 5	Visit 6	Visit 7
screening period	intraoperative (LAAO)	LAAO postoperative to discharge or 7 days postoperative	1 month after surgery (ablation)	Post-ablation to discharge or 7 days post-procedure	3 months after surgery	1 year after surgery	
informed consent	▲ ¹						
Inclusion/exclusion criteria	▲						
Demographic information	▲						
Medical history ²	▲						
Surgical information ³		▲		▲			
CHA ₂ DS ₂ -VASc score	▲						
HAS-BLED score	▲						
MRS Rating Scale ⁴	△		△		△	△	△
routine blood test	▲		▲		▲	▲	▲
Renal function ⁵	▲		▲		▲	▲	▲
Coagulation INR	▲		▲		▲	△	△

Evaluation of the Safety and Efficacy of Catheter Ablation Following Left Atrial Appendage Occlusion Using the WATCHMAN FLX Device

TEE	△		△		△	△	△
CT	△		△		△	△	▲
12-lead electrocardiogram ⁶	▲		▲		▲	▲	▲
Combined medication ⁸	▲		▲		▲	▲	▲
adverse event	▲	▲	▲	▲	▲	▲	▲

Remarks:

1. For the active collection of information, the examination items were completed according to the needs of patients' diagnosis and treatment evaluation and clinical research; △ For the selective collection of information, the researcher judged and chose to complete these examination items according to the actual health status of the patients, and this study did not intervene/require the patients to complete these examination items.
2. Medical history: including past medical history, family history, history of atrial fibrillation, personal history, medication history, surgical history, history of hypertension, diabetes mellitus, coronary artery disease, heart failure, peripheral vascular disease, history of hepatic and renal disease, stroke or systemic embolism, and cardiovascular-related surgery
3. Surgical information: intraoperative imaging such as DSA, other intraoperative information such as anesthesia, anticoagulant dosage, perioperative surgical complications, surgical approach, etc.
4. Evaluate when a neurological event occurs
5. Renal function: creatinine, creatinine clearance
6. 12-lead electrocardiogram: the most recent occurrence was recorded during both the screening and follow-up periods.

Combined medications: record of anticoagulants, antiplatelet agents, antihypertensive agents, lipid-lowering agents, hypoglycemic agents, and medications to treat surgical complications.

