	
3. Follow-up: Baseline patient data will be collected prior to the first procedure. Follow-up visits will occur within 7 days post-LAAO or at discharge, and at 1 month (i.e., time of the second procedure), 3 months, and 12 months post-procedure. Follow-up will focus on device endothelialization at 12 months, recurrence of atrial fibrillation, and occurrence of related complications.
 
Postoperative Medication Management Strategy:
 
Patients will receive anticoagulation therapy for 1 month following LAAO with the WATCHMAN FLX device. If no thrombosis or significant residual flow is detected, catheter ablation for atrial fibrillation will be performed. After the ablation procedure, anticoagulation therapy will be continued for an additional 2 months. Antiarrhythmic drugs (AADs) may be used within 90 days post-ablation in accordance with AF management guidelines.

Primary endpoint	The success rate of complete left atrial appendage (LAA) closure within 12 months following LAAO with the WATCHMAN FLX device, as assessed by LAA computed tomography angiography (CTA).
Secondary endpoint	
Safety Endpoints:
 
Incidence of procedure-related complications and adverse events within 30 days after LAAO and radiofrequency ablation, including rates of pericardial effusion, access site complications, vascular complications, and infections. The incidence of procedure-related complications and adverse events within 12 months following LAAO and radiofrequency ablation will be evaluated. These include major bleeding events (defined as those requiring blood transfusion or surgical intervention), cardiac tamponade, systemic embolism (including ischemic stroke and other embolic events), device-related thrombosis (DRT), new or enlarged peri-device leak (PDL, defined as >5 mm), acute postoperative left heart failure, and rehospitalization.
 
Efficacy Endpoints:
 
 1. Treatment success rate within 3 months after radiofrequency ablation (Early recurrence): No recurrence of atrial arrhythmias ≥ 30 seconds. 2. Treatment success rate between 4 to 12 months after ablation (Late recurrence): No recurrence of atrial arrhythmias ≥ 30 seconds during this period. 3. Incidence of stroke within 12 months following LAAO: No occurrence of stroke.

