6.1 Sample size calculation

The sample size was calculated based on the primary endpoint. The primary endpoint of this study was “12-month rate of complete closure of the block after WATCHMAN FLX LAAO (CT assessment)”.

Assuming that P_0 is the target incidence rate and P_1 is the trial incidence rate, P_0 was set to 74.3% (95% confidence interval: 65.9%~ 82.7%) based on the literature reports* and expert recommendations, the hypothesis testing was as follows:

$$H_0: P_1 \leq 0.743$$

$$H_1: P_1 > 0.743$$

A P_1 of 84.3% was set, significance level $\alpha = 0.05$ (one-sided), and test efficacy $1 - \beta = 80\%$. According to the sample size formula, 200 patients were needed in a single group to fulfill the statistical requirements. Considering a 5% loss-to-follow-up rate, the total sample size was set at 210 cases.

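### The two rhythm endpoints claim freedom from arrhythmia of 30 seconds or more over months, but the schedule as shown supports them with a few 12-lead ECGs, so apparent ablation success is biased upward by an unknown amount

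*Protocol*

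**What the plan says.** The Summary (Secondary endpoint, Efficacy Endpoints) has two rhythm endpoints. The first is "Treatment success rate within 3 months after radiofrequency ablation (Early recurrence): No recurrence of atrial arrhythmias ≥ 30 seconds". The second covers months 4 to 12 after ablation and requires "No recurrence of atrial arrhythmias ≥ 30 seconds during this period". Section 3.1.2 makes recurrence a named objective: "To investigate the impact of a two-surgery sequential treatment regimen on the recurrence rate of atrial fibrillation".

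In the Section 4.1 visit table, the row "12-lead electrocardiogram ⁶" is marked for active collection at Visits 1, 3, 5, 6 and 7. Remark 6 to that table reads: "12-lead electrocardiogram: the most recent occurrence was recorded during both the screening and follow-up periods". No Holter, patch, event recorder or device interrogation appears in the table or remarks as shown.

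The Summary places follow-up "at 1 month (i.e., time of the second procedure), 3 months, and 12 months post-procedure", in addition to the early post-procedure check. No visit is scheduled between 3 and 12 months.

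**The concern.** The endpoints are statements about whole intervals: no qualifying episode at any time in roughly three months, then none in roughly nine. The measurement is a handful of isolated tracings. A patient whose arrhythmia comes and goes can be in sinus rhythm at every visit and be classed as a success.

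Two features make this worse. Remark 6 does not require tracings taken between visits to be retained. And nothing says how arrhythmia seen on a 12-lead ECG counts toward a 30-second threshold, so sites may classify the same tracing differently.

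The error runs one way: a missed recurrence can only raise the success rate. These two endpoints are the trial's only rhythm measures of the ablation. As planned, the result would be labelled freedom from 30-second episodes, which is more than the recordings can show. An analysis plan cannot repair this later, because it cannot recover tracings that were never collected.

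**Working it through.** **Figures in the plan.** The protocol gives no assumed recurrence rate, detection rate or power for the rhythm endpoints, so there is no figure to reproduce.

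**Step 1: scheduled tracings per window (Section 4.1).** Visits 1 and 3 precede ablation. Three ECGs follow it:

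- Early window: Visit 5 (discharge or 7 days after ablation) and Visit 6 (3 months), so 2 tracings.
- Late window: Visit 7 (1 year), so 1 tracing.

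If the 3-month and 1-year visits are counted from the appendage procedure, Visit 7 falls about 12 − 1 = 11 months after ablation, and the last month of the late window has no scheduled test.

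**Step 2: the two readings of Remark 6.**

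- Latest ECG at each visit: the counts in Step 1 stand.
- One latest ECG for the whole follow-up period: a single tracing is kept, and the early window may have none.

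Under either reading, tracings between visits are not required.

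**Step 3: illustration of the bias.** Assumptions, none of them in the protocol:

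- True success S = 70%, so 30% recur.
- A patient with recurrence is in arrhythmia a share b of the time (the burden).
- The k ECGs in a window are independent, and arrhythmia on an ECG counts as recurrence.
- There is no symptom-driven or event-report detection.

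Probability of detection = 1 − (1 − b)^k. Apparent success = 1 − (1 − S) × [1 − (1 − b)^k].

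| Burden b | Late window, k = 1 | Early window, k = 2 |
|---|---|---|
| 5% | 1 − 0.30 × 0.05 = 98.5% | 1 − 0.30 × 0.0975 = 97.1% |
| 10% | 1 − 0.30 × 0.10 = 97.0% | 1 − 0.30 × 0.19 = 94.3% |
| 50% | 1 − 0.30 × 0.50 = 85.0% | 1 − 0.30 × 0.75 = 77.5% |
| 100% | 70.0% | 70.0% |

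In patients: 30% of 210 is 63 with late recurrence. One ECG misses 63 × 0.90 = 56.7, about 57, at 10% burden; 63 × 0.50 = 31.5, about 32, at 50%; and none if arrhythmia is continuous.

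**Step 4: sensitivity to the assumed success rate.** At 10% burden in the late window, S = 60% gives 1 − 0.40 × 0.10 = 96%, and S = 80% gives 1 − 0.20 × 0.10 = 98%. A true range of 20 percentage points shrinks to an apparent range of 2.

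**The case against.** Several objections have force.

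*Clinical recurrences have another way into the data.* Adverse events are collected at every visit. Section 8.1.1 covers worsening of an existing condition and names tachycardia and abnormal ECG findings, Section 8.1.3 requires all adverse events to be recorded, and rehospitalization within 12 months is itself an endpoint. A reader might infer that an ECG showing AF in month 7 is lost to the study. The documents do not support that. What stands is narrower: no text links those records to endpoints 1 and 2, and silent episodes would not surface there.

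*Remark 6 is loosely worded.* Taking it to mean that one ECG is kept for all of follow-up would conflict with the table, which marks the ECG at three post-ablation visits. The point does not depend on that reading.

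*A row may be missing.* The markers in the table run from 6 to 8 and no remark 7 is shown, so a lost row on rhythm monitoring cannot be wholly excluded. Nothing else in the text mentions longer monitoring.

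*A 12-lead tracing may be shorter than 30 seconds.* It is tempting to conclude that the ECG can never satisfy the definition. The protocol gives no tracing length, and under that reading apparent success would be 100% at every burden, which is not what the illustration assumes. The point rests on the coverage gap and the missing counting rule.

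*These are not the only efficacy measures of the ablation.* Correct: efficacy endpoint 4, the AFEQT score, also bears on it. Recurrence falls under the secondary purpose, and the sample size and hypothesis test concern appendage closure only.

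*Sustained recurrence would be caught.* Also correct, and entry is not limited to intermittent AF. But intermittent AF is not excluded either, and that is where spot tracings miss most.

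**Conclusion.** The point holds as a weakness in how two secondary endpoints are ascertained and labelled. The schedule as shown cannot support a claim of freedom from 30-second episodes over months. Any error from missed episodes inflates success.

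The direction follows from the documents; the size does not. The illustrated range for the late window, from no bias at 100% burden to 28.5 percentage points at 5% burden (98.5% − 70%), depends on an assumed 30% recurrence, on detection equal to burden, and on no recurrences being found outside the scheduled ECG. The last assumption makes the figures pessimistic.

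The primary closure test and its sample size are unaffected. The change should be made, preferably before follow-up data accumulate, because tracings that are not collected may not be recoverable.

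**What to change.** 1. **Definition.** State that recurrence is AF, atrial flutter or atrial tachycardia on any 12-lead ECG, or lasting at least 30 seconds on any longer recording.
2. **Collection.** Reword Remark 6 so that each visit records the visit ECG plus every ECG or other rhythm recording obtained since the previous visit, with date and rhythm. Count recurrences found through adverse event and rehospitalization reports toward endpoints 1 and 2. If a monitoring row or remark 7 exists, restore it.
3. **Label.** Report both endpoints as freedom from documented recurrence under visit ECG plus clinically obtained recordings. Give the number of recordings per patient and state that under-detection remains.

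This needs protocol and case report form wording and a little more data entry, but no new procedure. The reported success rate is likely to be lower and the label more modest. The changes reduce the bias without removing it, because months 4 to 12 would still have one scheduled tracing. A scheduled ambulatory recording would be stronger, but it is not needed to make the endpoint and its label agree.
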